## Tables

- Summary tables showing number and frequencies of participants for the following categories: no consecutive worsening; consecutive worsening; partial recovery; full recovery by category Motor function, DTR and Sensory and overall

**Table 2-4 Example of consecutive worsening and recovery for Neuro Exam**

Visit	Scenario 1 No consecutive worsening	Scenario 2 consecutive worsening followed by recovery	Scenario 3 consecutive worsening NOT followed by recovery
Baseline	normal	normal	normal
Wk1	normal	normal	normal
Wk2	decrease	decrease	normal
Wk3	normal	decrease	decrease
Wk5	decrease	normal	decrease
Wk9	normal	decrease	normal
Wk13	decrease	normal	decrease
...			

#### 2.7.4.5 Neuropathy questionnaire

For neuropathy symptoms: worsening is defined for participants with a change in answer from “No” at baseline to “Yes” at post BL.

Flags by visit and by parameter level:

- By visit flag 1: adverse change indicated by a “YES” response to the same question in the questionnaire in at least 2 consecutive visits. flag the last visit with finding
- By visit flag 2: adverse change indicated by a “YES” response to a question in the questionnaire at any post baseline visit
- By visit flag 3 (recovery): Flag visits after **last** visit with finding (this finding stands for any worsening and don’t have to be consecutive) that the answer is back to baseline

Flags by participant level based on the above visit-based:

- Participant level flag 1: Participant without any finding at 2 consecutive visits
- Participant level flag 2: participants with any finding at 2 consecutive visits

- Participant level flag 3 (recovery): participants with any finding at 2 consecutive visits and followed by recovery (finding no longer present in all worsened questionnaire)
- Participant level flag 4 (partial recovery): participants with any finding at 2 consecutive visits and followed by partial recovery (finding no longer present in at least one of the worsened questionnaire)
- Participant level flag 4: Participant without any finding at any visit
- Participant level flag 5: participants with any finding at any visit
- Participant level flag 6 (recovery): participants with any finding and followed by recovery (finding no longer present in all worsened questionnaire)

Participant level flag 6.5 (partial recovery): participants with any finding and followed by partial recovery (finding no longer present in at least one of the worsened questionnaire) Note that, flags will be created based on weekly basis window instead of protocol scheduled visit window.

## Tables

- Summary tables showing number and frequencies of participants with at least 2 consecutive worsening change, recovery and partial recovery
- Summary tables showing number and frequencies of participants with any worsening change recovery and partial recovery

## Listings

- Listing will be provided for participants with consecutive findings.

### 2.7.4.6 Nerve conduction study (NCS)

NCS are conducted at baseline and repeated in every patient as per USM.

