- Increased serum neurofilament light chain (sNfL) levels observed in more than half of the participants after 9 weeks on treatment
- Decreased amplitude in the sural nerve (SNAP) compared to baseline in the 3 participants with both an increase in sNfL and decreased or absent DTRs
- Paresthesia in the lower extremities was reported by two participants. One resolved on treatment within 5 days and one led to early treatment discontinuation and subsequently resolved.

In this communication:

Participants that were actively taking study treatment at the time were instructed to stop the study treatment immediately and to return to the site for an on-site visit no later than 7 business days after being informed of the USM. The USM letter provided details on the assessments to be conducted during that visit. Subsequent to this on-site visit participants were to continue to adhere to their monthly visit evaluation schedule for on-site visits as per protocol (e.g., Week 9, 13, 17, 21, 25 etc.) until further notice. During these visits, all scheduled assessments were to be performed as per protocol with the following exceptions:

- Study drug should no longer be taken by participants
- PK [REDACTED] including mHTT/HTT (plasma [REDACTED]) [REDACTED] should only be collected up to 6 weeks after the last dose of study drug. The 0-Hour timepoint (pre-dose in the protocol pre-USM) is the only required timepoint for collection.
- No additional lumbar puncture will be scheduled thereafter unless deemed necessary by the investigator.
- Follow-up Nerve Conduction Study (NCS) evaluation may be required on a case-by-case basis, in consultation with the DMC.

Participants that had already permanently discontinued study treatment and had scheduled an End of Treatment (EOT) and/or follow up assessments at the time of this USM were to continue the previously agreed upon schedule of assessments as per discussions between investigator and Sponsor.

Subsequently a **Follow-up IN (24-Oct-2022)** was sent to sites to provide an update on activities related to the ongoing study following the initial communication on 05-Aug-2022. No new changes were implemented as the purpose was to remind of the above schedule of assessments exceptions.

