As per the USM, participants were to continue with their original VES up to and including Week 29. A new VES was created for Weeks 33, 53 and 69 (see [Table 8-5](#)).

The assessment schedule ([Table 8-2](#), [Table 8-3](#) and [Table 8-4](#)) lists all of the assessments and when they are performed. All data obtained from these assessments must be supported in the participant's source documentation, as appropriate.

Participants should be seen for all visits/assessments as outlined in the assessment schedule or as close to the designated day/time as possible. Refer to [Table 8-1](#) for allowable visit windows. Missed or rescheduled visits should not lead to automatic discontinuation.

If the end of the Blinded Extension has not been triggered by the time participants reach week 53 (i.e., because the results of the DRF are not available), the BE will continue beyond week 53. Participants beyond Week 53 will remain on the assigned dose until the End of Blinded Extension is triggered. Refer to [Table 8-3](#).

The Baseline visit in the OLE is equivalent to the End of Treatment (EOT)-Blinded Extension visit for participants who are still ongoing at the time the End of the BE is declared. Investigators will be notified ahead of time in preparation for transition to OLE. Since the duration of the BE may be different for individual participants, and in order to minimize participant burden, guidance will be provided to Investigators to clarify what BE assessments may be deferred at the final regular BE visit to ensure that they are performed only once as part of the OLE baseline visit, such as LP and MRI.

If the COVID-19 or similar pandemic limits or prevents on-site study visits, alternative methods of providing continuing care may be implemented. Phone calls, virtual contacts (e.g. teleconsult) or visits by site staff/home nursing service to the participant's home depending on local regulations and capabilities, may replace on-site study visits, for the duration of the pandemic until it is safe for the participant to visit the site again. If the Investigator delegates tasks to an off-site healthcare professional, the Investigator must ensure the individual(s) is/are qualified and appropriately trained to perform assigned duties. The Investigator must oversee their conduct and remain responsible for the evaluation of the data collected.

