Weeks	-6 to -1	-1	1							2	3	5	9			13	17			
Time (post-dose)	-	-	0h	4h	7h	12h ²	22h	72h	-	-	-	0h	4h	12h ²	22h	-	0h	4h	7h	12h ²
HbA1c	X																			
NTproBNP, Troponin	X	X							X	X		X	X			X	X			
Coagulation Panel	X ³	X							X	X	X	X	X			X	X			
Follicle stimulating hormone - FSH ¹⁰		X														X				
Serum Bile Acid ¹¹		X											X							
Pregnancy Test - Serum	X	X										X	X			X	X			
Pregnancy Test (urine) ¹²			X							X	X									
Urinalysis ¹³	X ³	X							X	X	X	X	X			X	X			
Fasting glucose	X																X			
Columbia-Suicide Severity Rating Scale (C-SSRS)	X ³	X							X	X	X	X				X	X			
Serum Biomarkers (NfL and others) ^{14,21}	X	X							X	X	X	X				X	X			
Echocardiogram ¹⁵	X											X				X				
Nerve Conduction Studies (tibial nerve CMAP/sural nerve SNAP)	X		Only performed if positive findings on neurologic exam or per Investigator judgement																	
Ophthalmologic examination ¹⁶	X															X				
Brain MRI ^{17,18}		X														X				

Period	Dose Range Finding		Blinded Extension								
Visit Name	Wk 17 ¹		Wk 21	Wk 25	Wk 29	Wk 33	Wk 37	Wk 41	Wk 45	Wk 49	Wk 53 - EOT Blinded ^{26, 27, 28}
Days	113 to 116		141	169	197	225	253	281	309	337	365
Weeks	17		21	25	29	33	37	41	45	49	53
Time (post-dose)	22h	72h	-	-	-	-	-	-	-	-	-
Columbia-Suicide Severity Rating Scale (C-SSRS)			X	X	X	X	X	X	X	X	X
Serum Biomarkers (NfL and others) ^{14, 21}			X	X	X	X	X	X	X	X	X
Echocardiogram ¹⁵			X		X		X		X		X
Nerve Conduction Studies (tibial nerve CMAP/sural nerve SNAP)	Only performed if positive findings on neurologic exam or per Investigator judgement										
Ophthalmologic examination ¹⁶							X				X
Brain MRI ^{17, 18}						X					X
UHDRS - TFC, TMS, IS, [REDACTED] ¹⁷					X						X
Plasma (mHTT/total HTT) ²⁰	X	X		X ²¹		X ²¹		X ²¹			X ²¹
PK blood collection	X	X		X ²¹		X ²¹		X ²¹			X ²¹

13 Urine dipstick done at site; if findings then send urine to central lab for microanalysis

14 Serum Biomarkers, including NFL. See Biomarkers Assessments in Blood and CSF, [Section 8.5.3](#)

15 Echocardiogram with GLS

16 Indirect with scleral indentation (if necessary) and Direct ophthalmoscopy

17 To minimize burden to patients, it is recommended that Post-baseline MRI and UHDRS assessments are done up to 1 day prior to the planned study drug dosing date at any given visit. If done same day as Lumbar Puncture, MRI and UHDRS should be done first.

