Days	1	29	57	85	113	141	169	197	225	253	281	309	337	365	999
Weeks	1	5	9	13	17	21	25	29	33	37	41	45	49	53	143

that they are performed only once as part of the OLE baseline visit, such as LP and MRI.

² Participants who discontinue study treatment should be scheduled for an EOT Open-label visit at which time all of the assessments listed for the EOT open-label visit will be performed. A 30-day safety follow up period after the last open label study treatment dose was taken must be observed.

³ Findings must be recorded on the appropriate Adverse Events eCRF

⁴ Male patients only

⁵ Serum pregnancy test is collected as part of the blood chemistry. Refer to [Section 8.4.3](#) for positive result follow up action

⁶ Urine dipstick done at site; if findings then send urine to central lab for microanalysis

⁷ Echocardiogram with GLS

⁸ For visits where samples are collected only once a day, they must always be collected at approximately the same time of the day

⁹ Serum Biomarkers, including NFL. See Biomarkers Assessments in Blood and CSF, [Section 8.5.3](#)

¹⁰ Pre-dose

¹¹ Randomization will be done if there is more than one dose chosen

¹² IRT call and drug preparation by site personnel

¹³ Weekly dosing, not reflected on the VES, should be confirmed with weekly telephone calls to the participant and will be collected on the eCRF.

¹⁴ Update as necessary

¹⁵ To minimize burden to patients, it is recommended that Post-baseline MRI and UHDRS assessments are done up to 1 day prior to the planned study drug dosing date at any given visit. If done same day as Lumbar Puncture, MRI and UHDRS should be done first

The table below (see [Table 8-5](#)) reflects the changes in the USM follow-up notification dated 06-Dec-2022.

Participants randomized to placebo do not require additional safety assessments and can be discontinued from the study at the Week 33 visit or immediately if this visit was already completed. The End of Treatment and End of Study (EOS) dispositions can be declared. Participants that had already permanently discontinued study treatment and had scheduled an EOT and/or follow up assessments at the time of the USM follow-up notification dated 06-Dec-2022 should have follow up (FU) assessments as closely as possible to Assessment [Table 8-5](#).

Table 8-5 Assessment Schedule Urgent Safety Measure

Period	Revised follow-up assessment schedule ³			
Visit Name	Wk 33	Wk 53	Week 69	EOS
Days	225	365	477	477
Weeks	33	53	69	69
Physical Examination	S	S	S	

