Neurological Examination	X	X	X	
Vital signs (including body weight)	X	X	X	
Electrocardiogram (ECG)	X			
Hematology	X	X ¹	X ¹	
Clinical Chemistry	X	X ¹	X ¹	
Thyroid Function	X	X ¹	X ¹	
NTproBNP, Troponin	X	X ¹	X ¹	
Pregnancy Test - Serum	X	X	X	
Urinalysis	X	X ¹	X ¹	
Columbia- Suicide Severity Rating Scale (C-SSRS)	X	X	X	
Serum Biomarkers (NfL)	X	X	X	
Nerve Conduction Studies (tibial CMAP/sural nerve SNAP) ²	X	X	X	
Brain MRI	X	X	X	
UHDRS – TFC, TMS, IS, █	X		X	
Adverse Events	X	X	X	
Serious Adverse Events	X	X	X	
Prior and concomitant medications or therapies	X	X	X	
End of Study Disposition				X

Period	Revised follow-up assessment schedule ³			
Visit Name	Wk 33	Wk 53	Week 69	EOS
Days	225	365	477	477
Weeks	33	53	69	69

¹ To minimize burden to participants, it is recommended that safety labs/urinalysis are performed only if required for Adverse Events or follow up of an AE.

² NCS must be performed in triplicate and recommended bilaterally. However, if performed unilaterally, then it should be conducted on the same side as per the screening visit

³ Visit window for Week 33 onwards is ± 2 weeks.

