8.4.4 Neurological assessments

Neurological Examination

In addition to a standard neurological examination (mental status, cranial nerves I- XII, motor system, deep tendon reflexes, sensory system including touch and vibration, coordination, gait), a more detailed neurological examination comprised of motor system, deep tendon reflexes and sensory system will be completed and reported on a corresponding eCRF at BL and any clinically significant abnormalities will be noted at each visit.

Nerve conduction study (NCS)

As per the USM of 05-Aug-2022, if a repeat NCS is required due to findings suggestive of peripheral neuropathy, it is recommended that this be performed bilaterally with three separate readings. If it is performed unilaterally then it must be the same side as it was performed at screening.

Nerve Conduction Studies (NCS) are medical diagnostic tests to evaluate the function of motor and sensory nerves by measuring electrical conduction. NCSs will be conducted at screening and repeated in the event there are any new clinically significant findings during the neurological exam that might suggest peripheral neuropathy. The screening NCS results will be interpreted locally and should be normal without of any electrodiagnostic evidence of neuropathy.

This study will be assessing both the motor and sensory electrophysiological functions by testing the tibial and sural nerves respectively. The study will be performed unilaterally and the same side should always be assessed with three separate readings performed. The CMAP is recorded by electrical stimulation of a motor nerve. Its amplitude is measured in millivolts (mV). The SNAP is obtained by electrically stimulating a sensory nerve. Its amplitude is measured in microvolts (μ V). In addition, nerve conduction velocity (NCV) is taken during both tests. NCV indicates how quickly electrical impulses move along a nerve. It is measured in meters per second (m/s).

These tests will be performed by medical specialists at the site such as clinical neurophysiologists, or neurologists who subspecialize in electrodiagnostic medicine and who will be responsible in providing the final results and their interpretation.

The following tests will be assessed as safety parameters:

Table 8-9 Nerve conduction study safety parameters

Maximum of 3 measures performed per nerve
1a Sural SNAP Measurement #1 #2 #3
1b Sural Sensory NCV measurement #1 #2 #3
2a Tibial CMAP measurement #1 #2 #3

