**Table 2-5 Nerve Conduction Safety Parameters**

Maximum of 3 measures performed per nerve
1a Sural SNAP Measurement #1 #2 #3
1b Sural Sensory NCV measurement #1 #2 #3
2a Tibial CMAP measurement #1 #2 #3
3b Tibial Motor NCV measurement #1 #2 #3

Numbers with a/b refer to the fact that these measurements are yielded from one and the same stimulation.

There are four parameters included in NCS indicated in [Table 2-5](#), each will be measured three times on either laterality or both. For each parameter, per visit, the max value will be derived to calculate change from baseline:

Change = max (post-BL measurement #1, #2, #3) - max (BL measurement #1, #2, #3)

Note that, if a measurement is not repeated three times, max will be derived using available measurements (maybe less than three times).

The following flags and analyses will be created to capture worsening and recovery for each parameter by laterality: SNAP, sural NVC, tibial NCV and CMAP:

Flags by visit level:

- By visit flag 1:  $\geq 50\%$  reduction
- By visit flag 2 (recovery): For participants who met the criterion flag1 reduction  $\geq 50\%$ : Flag the visits after last visit with reduction  $\geq 50\%$  that the criteria (reduction  $\geq 50\%$ ) is no longer met

Flags by participant level for each parameter SNAP, sural NVC, tibial NCV and CMAP based on the above visit-based:

- Participant level flag 1: participants without any reduction  $\geq 50\%$  at any visit on any side
- Participant level flag 2: participants with a reduction of  $\geq 50\%$  at any visit on any side
- Participant level flag 3: participants with reduction of  $\geq 50\%$  at any visit and followed by recovery for all the side(s) that had worsening

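### SAP 2.7.4.6 assumes that every participant had a repeat nerve conduction study; the protocol did not ensure this, and an untested participant can be classed as having no reduction

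*SAP*

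**What the plan says.** **SAP.** Section 2.7.4.6 opens with "NCS are conducted at baseline and repeated in every patient as per USM". It then defines, for each nerve parameter, a visit-level flag for a fall of at least 50% and participant-level flags built on it. Participant flag 1, the no-event flag, covers "participants without any reduction" of that size at any visit on any side; it does not ask for a post-baseline test. The planned table gives numbers and frequencies without naming a denominator. Section 2.2 puts all non-PK analyses on the Safety Set, that is, everyone dosed.

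**Protocol, before Week 33.** The Core schedule (Table 8-2) has NCS at screening and afterwards "Only performed if positive findings on neurologic exam or per Investigator judgement". Section 8 says that after the Urgent Safety Measure (USM) "participants were to continue with their original VES up to and including Week 29". The Amendment 02 rationale reports the notice of 05-Aug-2022 as saying "Follow-up Nerve Conduction Study (NCS) evaluation may be required on a case-by-case basis, in consultation with the DMC". Section 8.4.4, citing the same notice, is also conditional: "if a repeat NCS is required due to findings suggestive of peripheral neuropathy, it is recommended that this be performed bilaterally with three separate readings".

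**Protocol, from Week 33.** Table 8-5, from the notice of 06-Dec-2022, marks NCS at Weeks 33, 53 and 69. Its footnote concerns technique ("NCS must be performed in triplicate and recommended bilaterally") and sets no trigger. The text above that table says "Participants randomized to placebo do not require additional safety assessments and can be discontinued from the study at the Week 33 visit", or at once if that visit was already done. Branaplam participants were asked to stay for about a year after their last dose.

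**The concern.** Neurotoxicity ended this programme, and NCS is its most objective measure of peripheral nerve function. If the SAP takes full re-testing as given, nothing in the tables will separate a participant who was tested and had no reduction from one who was never tested. A placebo rate of zero would then look like evidence of absence when it may be absence of evidence. In the active arm, the NCS rate also feeds the combined neurological findings table in SAP 2.7.4.7, which reports number and percentage with a finding.

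**Working it through.** **Step 1. Who can lack a repeat test?** Setting the passages side by side:

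| Period or group | Protocol source | Repeat NCS |
|---|---|---|
| All, up to Week 29 | Table 8-2; Section 8; Section 8.4.4; notice of 05-Aug-2022 | Triggered, by investigator judgement, or case by case |
| Branaplam, Weeks 33, 53, 69 | Table 8-5 | Scheduled, no trigger |
| Placebo, Week 33 not yet done in December 2022 | Text above Table 8-5 | No further safety assessments required; exit at Week 33 |
| Placebo, Week 33 already done in December 2022 | Same text | May leave at once; no scheduled repeat |
| Stopped treatment before the USM | Amendment 02 rationale; text above Table 8-5 | Previously agreed schedule in one place, as near as possible to Table 8-5 in the other |
| Withdrew from the study early | No specific rule for NCS | May have none |

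The clear structural gap is in placebo. In the active arm it is limited to participants who left before a scheduled test or followed another schedule.

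**Step 2. What do the SAP rules do with an untested participant?** Such a participant is in the Safety Set, has no visit with a fall of at least 50%, and so meets flag 1 as written. Side raises the same problem. Section 8.4.4 describes testing on one side, while the post-USM text recommends both. A side tested only after baseline has no computable change, yet it too shows no reduction.

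**Step 3. Illustration of size.** The documents give no NCS rate to reproduce and no number tested. Inputs: about 25 participants per arm (Protocol Section 3), 4:1 allocation (Section 6.3.2), and 7 active participants with a 50% fall in sural amplitude at the 2022 unblinded review (Amendment 02 rationale).

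- Planned active = 25 × 4/5 = 20; planned placebo = 25 × 1/5 = 5.
- Over all planned active: 7/20 = 35%.
- Over those tested, with the number tested assumed: 7/18 = 38.9%; 7/16 = 43.8%; 7/15 = 46.7%; 7/12 = 58.3%; 7/10 = 70.0%.

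**Step 4. Direction.** A tested-only rate is not automatically right, because early testing was largely prompted by findings. Suppose 10 of 20 were tested and the untested 10 have a true rate r. The full-group rate is (7 + 10r)/20:

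- r = 0: 35%
- r = 0.1: 40%
- r = 0.2: 45%

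The tested-only figure of 70% would overstate all three. For placebo, 0/5 and 0/3 both print as 0% but carry different information. With one event, 1/5 = 20% and 1/3 = 33%. If the active rate is held at 35%, the contrast is 15 points over all placebo and 2 points over those tested. Untested placebo participants in the denominator can therefore widen the contrast, while untested active participants in theirs can narrow it.

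**The case against.** The strongest reply is that Table 8-5 schedules untriggered NCS three times for branaplam participants, who were asked to stay about a year. For them the SAP sentence is broadly consistent with the protocol. The SAP dates from October 2023, so its authors may also have known who was tested. This stands for the active arm, but it does not cover placebo participants already past Week 33, and the SAP gives no count.

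Second, counting untested participants as event-free is a literal reading of flag 1, not an announced rule. Participant flags rest on visit flags. SAP 2.1.1 computes change only where both values exist, and SAP 2.5.4 and 2.6.4 leave missing values missing. The planned NCS table lists reductions and recovery, not flag 1 itself. This partly stands: a programmer could exclude the untested. However, those missing-value rules sit in the primary and secondary endpoint sections, and nothing in the NCS section tells the programmer to do so.

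Third, the report is abbreviated and descriptive, affected participants are listed, and the combined table in SAP 2.7.4.7 covers active participants only. That limits the consequence; it does not make the percentages interpretable.

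Stronger readings are tempting and not supported. A reader might infer that many participants were never re-tested; no passage gives the number. A reader might infer that the nerve-damage rate is understated; Step 4 shows that the direction depends on the denominator and on selection. A reader might say that each untested placebo participant moves the placebo rate by 20 points, as 1/5 suggests. Removing an untested participant from the denominator does not do that: 0/5 and 0/4 are both 0%, and 1/5 to 1/4 is 20% to 25%, a shift of 5 points.

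**Conclusion.** The coverage statement in SAP 2.7.4.6 conflicts with the protocol, and the rules built on it allow an untested participant or side to be reported as having no reduction. A zero or low NCS rate, especially in placebo, may reflect absence of testing. The extent is unknown because the number re-tested is not documented, and the direction of any bias in the active rate or in the active-placebo contrast cannot be determined from the documents. The figures of 35% (7/20) and 47% (7/15) only illustrate sensitivity to the denominator: 20 is planned rather than actual, 15 is assumed, and the 7 events come from the 2022 review, before the Table 8-5 schedule, and so are not the final numerator.

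**What to change.** - Replace the opening sentence of SAP 2.7.4.6 with a description that agrees with the protocol: triggered or case-by-case repeats before Week 33, scheduled repeats under Table 8-5, and the placebo exit rule.
- Limit flag 1 to participants with a baseline and at least one post-baseline NCS on the same side.
- Report the number assessed and a not-re-tested row by arm and parameter.
- Show rates over both the Safety Set and those assessed, since neither alone is safe.
- Present scheduled and triggered tests separately.
- Carry the number assessed for NCS into the combined table of SAP 2.7.4.7.

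The cost is SAP wording, a revised flag definition and a few table rows. No new data collection is needed, and no clinical procedure changes.
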